Responsibilities for the conduct and oversight for the trial are delegated to you as the Coordinating Principal Investigator. You may delegate trial related responsibilities to the listed Principal Investigator(s) and any trial-related personnel. All trial-related duties delegated by the Coordinating Principal Investigator or Principal Investigator(s) and trial-related personnel must only be delegated to those that are qualified by experience and training. The HammondCare Sponsor's Delegate and the HammondCare Research Governance Committee are to be notified of the following:

- Protocol deviation reports outlined in the HammondCare Research Complaints policy.
- Any serious breach of Good Clinical Practice, the clinical trial protocol, the clinical trial standard operating procedures, or the human ethics approval that is likely to affect to a significant degree the safety or rights of participants or the reliability and robustness of the data generated in the clinical trial.
- Significant safety issues that are likely to (or have the potential to) affect to a significant degree the safety or rights of participants or the reliability and robustness of the data generated in the clinical trial.
- Urgent safety measures implemented to remove or prevent a significant safety issue.
- Safety reports relating to the continuation, suspension, or discontinuation of the clinical trial for safety reasons.
- Non-compliance with the protocol, SOPs, GCP, and applicable regulatory requirement(s) significantly affects or can potentially affect human subject protection or reliability of trial results significantly.
- Participant complaints or concerns received concerning the conduct of the research.
- Significant modifications to the clinical trial are likely to affect a significant degree the safety or rights of participants or the reliability and robustness of the data generated in the clinical trial.
- Addition of participating trial sites, contractual arrangements at participating sites or modifications to legal agreements.
- The intention to conduct the trial in other countries.

4. Trial Objectives and Purpose

This research in context:

To place this clinical trial in context: HammondCare is a not-for-profit aged care provider. The Centre for Positive Ageing (a unit within the HammondCare Health and Palliative Care Business Unit) provides a large, allied health team that undertakes a range of community-based assessments and programs for older clients at risk of falling. The allied health team already provides some virtually delivered services to regional and rural NSW.

This research is to work alongside the Centre for Positive Ageing's allied health team to determine the ideal clinical model for a rapidly available, virtually delivered, allied health assessment service, able to reach a broader range of older people at risk of falls in a timely manner.

Aims:

The overarching aim of this study is to develop an evidence-based falls risk stratification algorithm and virtual model of service delivery for an Allied Health Professional (AHP) falls service. In summary, this research involves four phases; the first three of which are to develop the algorithm and virtual service delivery model, with the fourth and final phase being a small pilot study using the algorithm and model with consenting clients identified at risk of falls (based on the falls risk stratification algorithm), in which participants will be offered a virtually delivered AHP falls risk assessment. Community-dwelling aged care clients of HammondCare's community team (HammondCare At Home) will be those from whom the study population will be derived for the pilot phase.

The specific study aims are:

- (i) Conduct a scoping literature review on falls assessment protocols and algorithms, interventions, and risk minimisation evidence relevant to community-dwelling older adults.
- (ii) Develop an evidence-based falls risk stratification algorithm for use by community aged care staff, understanding the scope of practice of aged care workers.
- (iii) Collate and select a set of evidence-based falls risk assessments and interventions that could be delivered virtually by AHPs (referred to as the virtual AHP falls risk assessment throughout this protocol).
- (iv) Pilot the implementation of both the falls risk stratification algorithm and virtual AHP falls risk assessment to determine feasibility, suitability, and usability in the community aged care sector.

Research questions:

Will an evidence-based falls risk stratification algorithm and a structured, virtual AHP falls risk assessment, using evidence-based tools, (i) be perceived as suitable by community aged care staff and AHPs, (ii) be able to be practically deployed within a community aged care service, and (iii) be perceived to be acceptable to community aged care clients?

The primary endpoint to be measured during this study will be immediately post the three-month pilot of both the falls risk stratification algorithm and virtual AHP falls risk assessment (anticipated to be December 2024), but with some flexibility to extend the study dependent on the recruitment rate.

5. Background Information

In Australia, a significant majority (94%) of older adults reside in their own homes, with 23% receiving support through government-subsidised community aged care programs.¹ This figure is expected to grow as the Australian Government increases funding for these services.² Despite this, only a small fraction (2%) of these clients use AHP services like physiotherapy or occupational therapy.³ This is concerning, as these individuals are often at a heightened risk of falls due to factors such as limited mobility, reduced strength, and chronic pain.⁴ The lack of regular AHP input could contribute to the delayed identification of those community aged care clients at risk of falls, and thus missed opportunities for implementation of preventative strategies.

Falls are a leading cause of injury, accounting for 77% of hospitalisations and 71% of injury-related deaths among older Australians,⁵ with a cost of over AU\$2.3 billion to the healthcare system during the 2018-19 financial year.⁵ Timely access to AHPs could mitigate this, but current systems face challenges, especially workforce shortages and the logistical difficulties of providing in-home services, particularly in rural and remote areas. Growth in the number of direct care workers in aged care (nurses, AHPs and care assistants) is predicted to not keep pace with population ageing. If this occurs, there will be a shortfall of more than 110,000 direct care workers in the next decade, and 400,000 by 2050,⁶ further impacting timely access to AHPs. Additionally, community aged care workers, despite their regular and close contact with older clients, are not equipped with the training to conduct clinically-oriented falls risk assessments. This lack of specialised input can lead to delayed identification of clients at risk of falls, missing critical opportunities for early intervention.

Virtual care delivery has emerged as a promising solution, which have been well-received in several studies.⁷⁻⁹ However, critical gaps remain in effectively identifying those at the highest risk of falls, and in developing and evaluating virtual care delivery models to understand how best to deliver AHP assessments remotely. Best-practice guidelines recommend the use of falls risk stratification questionnaires/algorithms for this purpose.^{10, 11} The challenge lies in leveraging the vast existing network of community care workers who regularly interact with vulnerable older people, to screen and identify those at risk. Once identified, these at-risk people could then receive timely and skilled AHP assessment and management through a virtual, cost-effective manner.

References:

1. Australian Institute of Health and Welfare. Older Australians Canberra: AIHW; 2021 [updated 28/06/2023. AGE 87:[Available from: <https://www.aihw.gov.au/reports/older-people/older-australians/contents/about>.
2. Storen R. Aged care: Budget Resources Canberra: Commonwealth of Australia; 2023 [updated May 2023. Available from: https://www.aph.gov.au/About_Parliament/Parliamentary_departments/Parliamentary_Library/Budget/reviews/2023-24/AgedCare.

- [ICH Guidelines for Good Clinical Practice \(GCP\)](#)
- [National Statement on Ethical Conduct in Human Research](#) (National Statement)
- As approved by the Human Research Ethics Committee (HREC), the clinical trial protocol is responsible for monitoring the trial's conduct.
- The responsibilities set out by the HammondCare Sponsor's Delegate.
- The onsite or remote monitoring standard operating procedures as put in place by the clinical trial sponsor.

7. Trial Design

A mixed-methods four-phase study, with each phase informing subsequent phases has been selected to address the study aims (see Figure 1. Flow of trial stages):

Stage 1: Scoping literature review

The scoping literature review will consider current evidence on falls assessment protocols and algorithms, interventions, and risk minimisation relevant to community-dwelling older adults. It will directly inform the development of the rapid-response falls risk assessment and management service tool (falls risk stratification algorithm and virtual AHP falls risk assessment) and virtual model of delivery.

Stage 2: Community aged care staff and AHPs focus groups

Focus groups will be conducted with HammondCare at Home (HC@H) clinical and client care managers, and HammondCare Restorative Care Team AHPs. The focus groups will ensure that the rapid-response falls risk assessment and management service tool is not only theoretically sound but also practically applicable and able to be effectively delivered in the community aged care context, including within the scope of practice of community aged care staff (care worker, clinical manager, client care managers) and AHPs.

Stage 3: Rapid-response falls risk assessment and management service tool development

This stage focuses on development of the two components of the tool, building on insights from Stage 1 and 2:

- (i) A falls risk stratification algorithm that can be used by community aged care staff to identify deteriorating clients at an increased risk of falls. This could be either a paper-based or a dynamic questionnaire built into HC@H's client management software.
- (ii) Collation of a focussed set of evidence-based falls risk assessments and interventions that can be incorporated into an AHP assessment and able to be conducted virtually with the client (with the support of a HC@H staff member present in the home if needed).

Once the tool has been developed, participants (i.e. HC@H clinical and client care managers, and HammondCare Restorative Care Team AHPs) will be asked to work through real-world case scenarios using either the falls risk stratification algorithm (HC@H care workers and clinical and client care managers) or the virtual AHP falls risk assessment (HammondCare Restorative Care Team AHPs) then participate in an interview with a member of the research team to discuss the component of the tool they reviewed.

Stage 4: Pilot of the rapid-response falls risk assessment and management service tool

This stage will assess the practicality and effectiveness of the developed tool in a community aged care service, incorporated into routine practice (when indicated). The falls risk stratification algorithm will be pilot tested by HC@H staff and clients; the virtual AHP falls risk assessment to be pilot tested by HammondCare Restorative Care Team AHPs and clients, with the support of a HC@H care worker or manager being present in the home.

The piloting of both the falls risk stratification algorithm and virtual AHP falls risk assessment will include a focus on the clinical utility, user acceptance, and ability for the rapid-response falls risk assessment and management service tool to be incorporated into routine practice. Pilot data will be collected from clinical records, an anonymous online survey completed by HC@H staff and HammondCare Restorative Care Team AHPs at the end of Stage 4, and an online Patient-Reported Experience Measure (PREM) survey (a paper-based alternative will be provided if needed/request) completed by HC@H clients after completion of their participation in Stage 4. The PREM survey will not be anonymous to allow for linkage with client demographic and clinical outcome data during the analysis stage.

Once the virtual AHP falls risk assessment has been completed, the AHP's recommendations will be reported back to the client's HC@H clinical or client care (as appropriate) manager. Potential options may include a virtually delivered falls prevention program, a face-to-face AHP visit, liaison with GP or other usual care, which are all currently available services from HammondCare and are not the subject of this research (which is focussed on the development and pilot of the falls risk stratification algorithm and the virtual AHP falls risk assessment).

[figure not shown]

Figure 1. Flow of trial stages

8. Sample Size

Across Stages 2-4 HammondCare staff and clients will be enrolled in this study. HammondCare staff can consent to be involved in multiple stages. The target sample sizes for each stage are:

Stage 2:

Based on current literature, the target sample size is 18 (two to three focus groups of six to eight participants per group).¹² Ideally the sample size will be evenly distributed across the two participant groups: nine HC@H managers (a mix of clinical and client care managers), and nine HammondCare Restorative Care Team AHPs (a mix of physiotherapists, occupational therapists, and exercise physiologists).

Stage 3:

Based on other interview and survey studies, the target sample size is 22.¹² To ensure both components of the rapid-response falls risk assessment and management service tool are equally reviewed the sample size will be evenly split to include 11 HC@H staff (a mix of care workers, and clinical and client care managers) and 11 HammondCare Restorative Care Team AHPs (a mix of physiotherapists, occupational therapists, and exercise physiologists).

Stage 4:

The client target sample size is 13 HC@H community aged care clients, based on an anticipated referral rate of one per week (determined by staff feedback) over a three-month period. Potentially not all participants will require a virtual AHP falls risk assessment (dependent on the outcome of the falls risk stratification algorithm). To ensure sufficient data is collected for both components of the rapid-response falls risk assessment and management service tool a minimum of 50% of participants will need to have completed both the falls risk stratification algorithm and virtual AHP falls risk assessment. Therefore, recruitment will continue beyond the target sample size of 13 until the 50% minimum for completion of both components of the rapid-response falls risk assessment and management service tool is reached.

The staff target sample size is 13, based on recruitment of at least one member of staff per client participant (i.e. based on the falls risk stratification algorithm outcome for each client participant, a virtual AHP falls risk assessment may/ may not be indicated).

9. Selection and Withdrawal of Subjects

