9.5 Consent

Stages 2 and 3:

Stage 2 and 3 participants will be able to contact the research team to answer any questions they have before providing consent to participate in this study (using contact details provided in the recruitment email and information shared in staff/team meetings). At this time they will also be provided with a PISCF, and complete the screening questions (as outlined above in the *screening* section). They will have a one-week period to consider their participation and provide consent. This timeframe was considered sufficient whilst preventing delays in the completion of the study as both Stages 2 and 3 are required to inform subsequent stages and thus the development of the rapid-response falls risk assessment and management service tool. If they then decide to participate, they will be asked to sign and complete the consent portion of the PISCF (paper-based or electronic) and return it to the research team prior to data collection either by emailing it to the researchers or returning it to the researchers' office based at HammondCare (in person or the internal mail system).

Stage 4:

Consent from client participants will be obtain verbally by a HC@H clinical or client care manager who is not involved in the direct care of the client (Figure 2. HC@H client recruitment

and consent process). Verbal, informed consent will be obtained during a phone call to discuss the study and screen the client's eligibility, as a means of being able to deliver a rapid response virtual service (within 48 hours of client being identified as a potential participant for this study). Prior to this phone call, the PIS will be provided to the client by HC@H staff so the client has this to refer to during the phone call. This process will occur after the falls risk stratification algorithm developed in this study has been deployed by HC@H staff during routine care (as detailed above in the *recruitment* and *screening* sections). The confirmation of verbal consent by the client will be audio recorded, and then securely stored in the *verbal consent confirmation* folder. Consent will be reconfirmed by the client when they complete the online (or paper-based equivalent) survey by clicking the 'I agree, start survey' button at the bottom of the consent declaration page (first page) of the survey (this must be selected in order to start the survey).

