A phenomenology methodology will be adopted for the analysis of qualitative data from all stages (transcripts from focus groups, interviews, and open-ended survey responses). This approach is designed to capture the lived experiences and perceptions of participants, focusing on their subjective experiences and interpretations. Thematic analysis using an inductive framework will be conducted to identify, analyse, and report themes within the data in NVivo. Two investigators will independently code the data, grouping similar content into themes that emerge directly from the data. A third investigator will review discrepancies to ensure consensus is reached.

Quantitative analysis:

Descriptive methods in SPSS will be used to summarise the client demographics and PREM survey results to get an overview of participant characteristics, participant experiences, and user acceptance. Clinical utility and operational feasibility will be considered through analyse of frequency of falls risk stratification algorithm use, time taken to complete assessments, recruitment rates, assessment outcomes and recommendations (relevant to the pilot stage), and falls incidence.

15. Data Ownership

All research data collected during this trial is governed and handled following the Research Communications and Reporting Protocol and the SharePoint Document Management policy. HammondCare, rather than any individual or Organisational Unit, is the Custodian of data and materials and any information derived from the data. Original research data and primary materials generated in the research conducted within HammondCare services will be owned and retained by HammondCare subject to any contractual, statutory, ethical, or funding body requirements.

16. Handling and Reporting Data

Principal Investigators are responsible for maintaining adequate and accurate source documents and trial records that include all pertinent observations on each site's trial subjects. Source data must be attributable, legible, contemporaneous, original, accurate, and complete.

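### The Stage 4 rule to recruit past 13 until half have completed both components has no cap, may never be met if true uptake is below 50%, and pushes the observed uptake upward when it is met

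*Protocol*

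**What the plan says.** Section 8, Stage 4, gives the target: "The client target sample size is 13 HC@H community aged care clients". The figure rests on expected accrual, being "based on an anticipated referral rate of one per week (determined by staff feedback) over a three-month period". The section accepts that some clients will stop after the first component: "Potentially not all participants will require a virtual AHP falls risk assessment (dependent on the outcome of the falls risk stratification algorithm"). The purpose of the rule follows, "To ensure sufficient data is collected for both components of the rapid-response falls risk assessment and management service tool", and then its form: "a minimum of 50% of participants will need to have completed both the falls risk stratification algorithm and virtual AHP falls risk assessment". If that is not achieved at 13, "recruitment will continue beyond the target sample size of 13 until the 50% minimum for completion of both components" is reached. Section 8 states no maximum number of clients, no latest date and no action if 50% is not reached.

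Four other places bear on the rule:

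- Section 4 (Research questions) places the primary endpoint straight after a three-month pilot, anticipated for December 2024. It allows some extension depending on the recruitment rate.
- Section 9.5 says of the consent call: "This process will occur after the falls risk stratification algorithm developed in this study has been deployed by HC@H staff during routine care". Every consented client has therefore already had component one.
- Section 10, Stage 4, has clients complete the experience survey after either component. Clients who have only the algorithm are therefore participants.
- Section 14 (Quantitative analysis) says "Clinical utility and operational feasibility will be considered through analyse of frequency of falls risk stratification algorithm use". It goes on to list assessment times, recruitment rates, assessment outcomes and recommendations, and falls incidence.

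**The concern.** Having enough data on the virtual assessment depends on how many clients complete it, not on what share of all participants they form. Because the algorithm comes before consent, completing both components amounts to completing the virtual assessment. Clients for whom the algorithm does not indicate it, or who lack connectivity, can never become completers, yet they count in the denominator.

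Two consequences follow. First, if the true share of completers is below one half, each further client lowers the ratio on average, so continued recruitment is not a dependable remedy and the pilot has no guaranteed end. Second, recruitment stops on the observed share, so a share taken at the stop is selected to be 50% or more. At stake are a bounded enrolment plan and an honest uptake figure, if one is reported among the Section 14 feasibility summaries.

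**Working it through.** **Inputs.** Target 13, one referral per week, three months and the 50% minimum all come from Section 8. The probability p that a participant completes the virtual assessment is not in the protocol; I assume 0.30 to 0.70, constant p and independent clients.

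**The plan's own figure.** Three months is 3 × 52/12 = 13.0 weeks. At one client per week that gives 13, so the target reproduces and is not in dispute.

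**Step 1: rule met at 13.** Half of 13 is 6.5, so 7 completers are needed (7/13 = 53.8%). The chance is P(X ≥ 7) with X ~ Bin(13, p).

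**Step 2: rule met later.** With x < 7 completers at 13, the deficit is 13 − 2x. Each new client moves it by one step in either direction. The chance of ever closing it is (p/(1−p))^(13−2x) for p < 0.5, and 1 for p ≥ 0.5. At p = 0.40 the ratio p/(1−p) is 2/3:

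| x at 13 | P(x) | deficit | P(ever closed) | product |
|---|---|---|---|---|
| 6 | 0.197 | 1 | 0.667 | 0.131 |
| 5 | 0.221 | 3 | 0.296 | 0.066 |
| 4 | 0.184 | 5 | 0.132 | 0.024 |
| 3 | 0.111 | 7 | 0.059 | 0.006 |
| 0 to 2 | 0.058 | 9 to 13 | at most 0.026 | 0.001 |

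The products sum to 0.229. Adding the 0.229 already met at 13 gives 0.458 ever met and 0.542 never met.

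**Step 3: observed share at the stop.** A stop at 13 gives at least 7/13. A later stop comes when the deficit reaches zero, so the share is exactly 50%. The mean given that the rule is met is [P13 × m13 + (Pever − P13) × 0.5] / Pever, where m13 is the mean share among pilots that stop at 13. At p = 0.40, m13 = 0.585, so the mean is (0.229 × 0.585 + 0.229 × 0.5) / 0.458 = 0.543.

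**Results** (figures by 26 and 52 clients from an exact recursion):

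| p | met at 13 | met by 26 | met by 52 | never met | mean observed share if met |
|---|---|---|---|---|---|
| 0.30 | 6% | 12% | 12% | 87.5% | 53% |
| 0.40 | 23% | 41% | 44% | 54% | 54% |
| 0.45 | 36% | 59% | 65% | 29% | 55% |
| 0.50 | 50% | 75% | 83% | 0% | 56% |
| 0.60 | 77% | 95% | 99% | 0% | 62% |
| 0.70 | 94% | 99.6% | 100% | 0% | 70% |

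At p = 0.50 the rule is met eventually, but in 17% of pilots it is still unmet at 52 clients, about a year at one per week. The upward bias is about 23 points at p = 0.30, 14 at 0.40, 6 at 0.50, 2 at 0.60 and under 1 at 0.70.

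**The case against.** The strongest reply is that this is a small, descriptive, single-arm pilot with no test and no progression threshold, and that the 50% is only a floor for data sufficiency. Several parts of that stand.

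- The share completing both components is not named as an endpoint in Section 4 or Section 14.
- A reader might infer that a share below 50% means the model is infeasible. The protocol does not support that: Section 8 itself says the assessment may simply not be required, and Sections 9.3 and 10.1 send such clients to usual care by design.
- A reader might also infer that the pilot cannot return an unfavourable answer. That goes too far. Staff surveys, the client experience survey and the qualitative data can be negative at any ratio, and an overrun would show in the recruitment rates.
- Clients enter because staff have noticed deterioration, a fall or a near miss (Section 9.3), so p may be high. At 0.60 or above the harm is small.
- Extension is not futile below one half. It raises the chance of meeting the rule from 23% to 46% at p = 0.40, and from 36% to 71% at 0.45.
- Section 4 gives a time frame.

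What does not stand is that these points make the rule safe. The time frame is soft, and its extension is tied to the recruitment rate rather than to the 50% condition. Nothing in the protocol supports p of at least 0.5, and Section 8 plans for a shortfall. The rule is also stated in the protocol, so it is not detail left for an analysis plan.

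**Conclusion.** The point holds at moderate severity. Section 8 serves a count-type aim with an uncapped ratio. If true uptake is below 50%, recruitment may never satisfy it (29% of pilots at p = 0.45, rising to 87.5% at 0.30). Whenever it is satisfied, the observed share is 50% or more whatever the truth, so an uptake figure taken at that stop is biased upward when p is near or below 0.5.

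The size rests on an assumed p, on independent clients and on the rule being applied literally. Data withdrawn later (Section 9.6), or clients enrolled but not yet assessed at the stop, could move the final figure slightly below 50%. The finding concerns the end of recruitment and any uptake statement. It does not show that the pilot's conclusions on suitability or acceptability are predetermined.

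**What to change.** Replace the ratio in Section 8 with a minimum number of virtual-assessment completers, for example 7 (50% of 13, rounded up). Add a maximum number of clients or a closing date, chosen by the sponsor, whichever comes first. Align the extension wording in Section 4 with it.

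Report uptake with an exact 95% CI in the first 13 consecutively enrolled clients, whose number does not depend on the outcome. Separate three groups of non-completers: assessment not indicated; no connectivity or assessment declined; indicated but not completed. Use later clients for the experience survey, staff survey and qualitative data.

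A count of 7 always ends for any p above zero, after 7/p clients on average: 23.3 at p = 0.30 and 17.5 at 0.40, before the minimum of 13 is applied. With a purely illustrative cap of 26, it is reached in 70% and 94% of pilots respectively. This is a looser requirement than 50% (7/26 = 27%), but it is the one that matches the stated purpose.

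The cost is one paragraph, settled before Stage 4 recruitment. At the cap there may be fewer completers than the target count, which should be reported as a result. The estimate from 13 clients will also be imprecise: 7/13 has an exact 95% CI of about 25% to 81%.
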